### **Test of Proportionality Assumption**

This piecewise exponential model assumes proportional hazards for the treatment groups over time, in particular that the baseline hazard is constant within each period. The proportional hazards assumption will be assessed by fitting the same primary outcome model with a treatment by time interaction and tested via the likelihood ratio test at the 0.05 significance level. The treatment by time interaction term will be derived as the product of the reference cell coded surgical intervention variables and time where time is derived transforming censoring intervals to a single time measure as follows:

- time = lower bound of the censoring interval, if subject is right censored (i.e. lower bound is nonmissing and upper bound is missing)
- time = midpoint of the censoring interval, else if subject is interval censored (i.e. lower bound < upper bound, both non-missing) or not censored (i.e. i.e. lower bound = upper bound, both non-missing)

If the proportionality hazards assumption is violated, additional graphic analyses will be generated to help understand how the proportionality assumption was violated. A figure will be generated of the fitted PWE model estimates and 95% confidence bands for failure probability overlaid with failure probability estimates obtained by nonparametric methods for interval censored data stratified by surgical intervention (see Nonparametric Survival Analysis for Interval-Censored Data below). Through the same nonparametric survival analysis method for interval censored data, a figure will be generated of the hazard functions for the three surgical arms using smoothed Epanechnikov kernel estimation. These two figures will be studied closely to identify approximate time interval(s) where the hazard ratios are distinctly different. If this departure can be characterized as quantitative rather than qualitative using the terminology used by Gail and Simon to describe interactions, then this finding indicates that the relative risk is of a different magnitude at different time points, but that

relative risk doesn't change direction at any time point. Therefore, describing the surgical effect as an average effect over the full time period is a reasonable and clinically meaningful approach. However, if the hazard functions are not only different, but substantially cross then this departure is characterized as qualitative and alternative parametric models that better fit the relatively complex hazard structures will be explored and compared to the pre-specified primary model. If this is the case, an addendum to the SAP will be written describing the new model-based efficacy analysis methods.

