### Clarification to Section 9.4.2 Test of Proportionality Assumption:

Due to limitation of the SAS procedure and the use of the ID statement, the likelihood ratio test was conducted comparing nested semi-parametric interval censored models analogous to the primary efficacy analysis methods (but further relaxing the piecewise constant hazard assumption to be unspecified--no parametric assumptions made on the baseline hazard only that it is proportional).

Addition to Section 9.4.3 Sensitivity Efficacy Analyses of Primary Outcome

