### Post-hoc Sensitivity Analysis excluding data after the 3 year visit

A sensitivity analysis of the primary outcome through the primary endpoint excluding data after the 3 year visit on the primary analysis population will be conducted to evaluate the proportional hazards assumption during the first 3 years. Failure probability, hazard rate, and hazard ratio estimates and their corresponding confidence intervals and p-values are from an interval-censored proportional hazard model with an assumed underlying piecewise exponential hazard with three constant-hazard periods: [0, 12], (12, 24], (24, 36]. Excluding follow-up years 4 and 5 removed 14 events (2 events in NTR, 5 events in SC, and 7 events in TVM). The proportional hazards assumption is not violated in the MITT population (p=0.155).

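### The SAP's proportional-hazards test multiplies arm by each woman's own failure or censoring time, so as written it rejects even when hazards are proportional, and SAP 12 does not say how time was coded in the test behind p=0.155

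*SAP*

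**What the plan says.** Under Test of Proportionality Assumption, SAP 9.4.2 plans to check the assumption by "fitting the same primary outcome model with a treatment by time interaction and tested via the likelihood ratio test" at the 0.05 level. The interaction "will be derived as the product of the reference cell coded surgical intervention variables and time where time is derived transforming censoring intervals" into a single measure per woman. For a woman without failure that measure is the lower bound of her interval, her last attended visit. For a woman with failure, "time = midpoint of the censoring interval, else if subject is interval censored". Nothing in the section describes a term that changes as follow-up accrues within a woman.

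A rejection leads first to figures. Only "if the hazard functions are not only different, but substantially cross then this departure is characterized as qualitative", and then alternative models are explored and an addendum is written.

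SAP 12 (version 2) says: "Due to limitation of the SAS procedure and the use of the ID statement, the likelihood ratio test was conducted" by "comparing nested semi-parametric interval censored models analogous to the primary efficacy analysis methods", while "further relaxing the piecewise constant hazard assumption to be unspecified--no parametric assumptions made on the baseline hazard only that it is proportional". A post-hoc analysis that drops data after the 3-year visit then concludes: "The proportional hazards assumption is not violated in the MITT population (p=0.155"). That analysis removed 14 late events.

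**The concern.** A treatment-by-time term has to let the hazard ratio change as study time runs. The SAP's *time* is instead fixed for each woman and taken from her own result. A long value means late failure or none, so the covariate predicts the outcome by construction. A likelihood ratio test on it measures that built-in link, not departure from proportionality.

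At stake is what the diagnostic is worth. If the rule is applied as written, it always signals a violation and carries no information. If something else was run, the reader needs to know what it was before giving weight to the statement that proportionality is not violated.

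**Working it through.** **1. Inputs, checked against the plan's own figures.** From SAP 6: 2-year success of 80%, 60% and 65% gives yearly hazards −ln(S)/2 of 0.1116, 0.2554 and 0.2154, and a margin of 0.2154/0.1116 = 1.93. With uniform 2-year accrual, 3 years' minimum follow-up and 5% yearly loss, the mean failure probability in a mesh arm is 0.3264, so 242 × 0.3264 = 79.0 events in SC and TVM together. Schoenfeld power at one-sided 0.03 is Φ(√(79.0/4) × ln 1.93 − 1.881) = Φ(1.04) = 85.1%. The stated 85% is reproduced, so these hazards and this follow-up are a fair basis for simulation.

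**2. Why the written rule must reject.** A woman who fails at T contributes about h·exp(−hT), which is largest at h = 1/T and so falls as T grows. A censored woman contributes exp(−hT), largest as h goes to 0, and censored women tend to have the longest T. A covariate equal to T therefore takes a strongly negative coefficient whatever the shape of the hazard. In simulation at the design hazards it was about −1.7 per year.

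**3. Rejection rates when hazards are exactly proportional.** 121 women per arm, 6-monthly visits, first lower bound 1.5 months, follow-up uniform over 36 to 60 months, 5% yearly loss, interval-censored piecewise-exponential likelihood, 400 trials per set-up. Assumptions not from the documents: 5% missed visits, and no site or age terms. The 36-month cut uses six 6-month baseline pieces as a stand-in for an unspecified baseline.

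| Set-up | Written rule (smallest LR) | Arm × study time, 2 df | Arm × three periods, 4 df |
|---|---|---|---|
| Design hazards | 400/400 (138.7) | 26 (6.5%) | 23 (5.8%) |
| Design, late hazard × 0.73 (mean 15.0 failures after year 3) | 400/400 (141.1) | 32 (8.0%) | 23 (5.8%) |
| All arms 0.15 | 400/400 (183.9) | 20 (5.0%) | 28 (7.0%) |
| Design, cut at 36 months | 400/400 (130.4) | 19 (4.8%) | 21 (5.3%) |

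A separately coded simulation (eight settings, 300 trials each) gave 100% for the written rule in every setting, including those with the baseline left free per visit interval, the form nearest to SAP 12. A time-dependent term rejected in 3.7% to 7.3%. Relaxing the baseline does not cure the fault.

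**4. What p=0.155 requires.** On 2 df, LR = −2 ln(0.155) = 3.73. The smallest LR from the written rule, over proportional and crossing set-ups together, was 100.4, which corresponds to p = exp(−50.2), about 2 × 10⁻²². On 4 df, p=0.155 needs LR = 6.66.

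**5. Power of the two replacements when hazards cross** (rejections, full follow-up / 36-month cut).

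| Pattern | Arm × study time | Arm × three periods |
|---|---|---|
| X1: TVM:SC ratio 0.5 in year 1, then 3.0 | 75% / 88% | 96% / 95% |
| X2: ratio 0.5 to month 18, then 2.0 | 76% / 79% | 62% / 59% |
| X3: NT hazard 0.383 in year 1, then 0.067 | 93% / 96% | 98% / 96% |
| X4: SC 0.06 then 0.16, TVM 0.20 then 0.06, switch at month 12 | 86% / 85% | 93% / 93% |

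**6. A hypothetical variant, not in the SAP.** If own time were also entered as a main effect in both nested models, the test would be conservative under proportionality (0.5% to 3.8% in these set-ups; 1 of 300 in the second simulation) and weak against crossing (10% to 30%). Under crossing, p of 0.155 or more would arise in 37% to 76% of trials, against 1% to 10% with arm by study time. This shows only that the value of p=0.155 depends on a coding the documents do not give.

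**The case against.** The best case against the point is that version 2 already clarified this test, that 0.155 cannot have come from the literal rule, and that what remains is an undocumented detail of a diagnostic. A rejection leads only to figures. Smoothed hazards are assessed in any case under the nonparametric analysis in SAP 9.4.3, and hazard and log-cumulative-hazard displays are listed in SAP 14. A change of model depends on judging that the curves substantially cross. SAP 9.4.2 also already tests the primary model, which runs to 60 months, so a full-follow-up check is planned.

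Most of this stands, and it limits the consequence. It does not remove the point. SAP 12 describes a change to the baseline and mentions an ID statement, which does not appear in the model code listed in 9.4.2. It neither withdraws nor replaces the own-time covariate, and a freer baseline leaves the fault in place.

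Stronger readings are tempting. A reader might infer that p=0.155 is wrong, that crossing hazards were hidden, or that the full-follow-up test failed. The documents support none of these: a correct time-dependent term may have been fitted, the masking variant is hypothetical, and no full-follow-up result is given in either direction.

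**Conclusion.** The rule written in SAP 9.4.2 is not a 5% test of proportional hazards. It rejected in every simulated trial with proportional hazards, and a contrast of 100% with roughly 5% to 8% should not hinge on the missed-visit rate or the omitted covariates. The p=0.155 in SAP 12 almost certainly came from some other test, whose validity cannot be verified from the documents.

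The effect is confined to this diagnostic and the steps it triggers. A reader might go on to doubt the confirmatory results; that does not follow, because none of the four confirmatory hazard ratios uses this term and the graphical and nonparametric checks remain. It should be fixed, but it is not critical.

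Either replacement is acceptable. Their power differs by crossing pattern, and arm by study time was somewhat liberal in one set-up (32/400, 95% CI 5.5% to 11.1%).

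**What to change.** - In SAP 9.4.2, delete the subject-level *time* covariate. Test the primary model against a genuinely time-dependent term: arm by study time (2 df), or arm by collapsed periods such as 0–12, 12–36 and 36–60 months (4 df). For the 3-year cut, arm by the three yearly periods serves.
- In SAP 12, state the time coding, degrees of freedom and ID-statement set-up behind p=0.155, and rerun that test if the own-time covariate was used.
- Report the full-follow-up result that 9.4.2 already calls for, beside the 3-year cut, in each primary population: Per-Protocol for Aim 1, MITT for Aim 1a, and MITT-narrow for Aims 2 and 3 where it is used.
- Keep the planned graphical and nonparametric checks.

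The cost is one SAP paragraph and one extra model fit per population. No new data are needed, and no confirmatory test or hazard ratio changes.

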PGI-I

Global Improvement:

SF-12 and subscales

Although the GCO will not be reported as a secondary outcome, the following points will be considered a priori as a failure in order to develop structure for the exploratory aim and future development of a GCO.

Safety/Adverse Events:

Dindo Complication Scale Class III and IV and CTCAE Grades 3 and 4

Regret/Satisfaction:

• DRS-PFD (a "strongly agree" or "agree" response to regret Question 2)

Condition Specific Improvement:

PGI-I (a response of "very much worse" or "much worse")

Global Improvement:

SF-12 (worsening of utility scores from baseline)

M. STATISTICAL CONSIDERATIONS AND ANALYTICAL PLAN

M.1. Sample Size/Power Calculations

Sample size calculations were generated under the assumptions that the three study arms are: 1) mesh augmented sacral colpopexy, 2) transvaginal mesh repair, and 3) native tissue repair for vault prolapse. Further assumptions were that the study would have an overall Type I error rate of 0.05, that a randomization ratio of 1:1:1 is preferred for feasibility reasons, and that the Type I error (alpha) would be distributed among the following three hypotheses related to the 3 treatment arms in a way that optimizes sample size and at the same time is scientifically defensible:

- H1: transvaginal mesh is non-inferior to mesh augmented sacral colpopexy [spend alpha of 0.03 using a one-sided non-inferiority test]
 - H1a: transvaginal mesh is superior to mesh augmented sacral colpopexy [spend alpha of 0.03 using a two-sided test of superiority]
- H2: mesh augmented sacral colpopexy is superior to native tissue repair [spend alpha of 0.01 using a two-sided test of superiority]
- H3: transvaginal mesh repair is superior to native tissue repair [spend alpha of 0.01 using a two-sided test of superiority]

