The sample size estimates also assume that the primary analyses for each of the three hypothesis tests will be based on a survival analysis model with a 2-year recruitment period and a 3-year follow-up period after the last participant is randomized and that loss to follow-up on each arm will be no more than 5% per year, that the 2-year success rates for mesh-augmented sacral colpopexy and transvaginal mesh repair will be 80%, and that the 2-year success rate for native tissue will be 60%. These 2-year success rates represent hazards of 0.1116 and 0.2554, respectively, under the assumption that the failures follow an exponential survival model. For the non-inferiority margins, the analyses two-year 15% margin; this non-inferiority margin corresponds to a hazard ratio of 1.93.

Under the assumptions outlined above, the hypothesis test that drives the sample size is the test on non-inferiority of transvaginal mesh to mesh-augmented sacrocolpopexy. A sample size of 121 participants per arm will provide 85% power to demonstrate non-inferiority under the assumptions outlined above. Assuming that 121 participants will also be randomize to native tissue repair, the overall sample size of 363 participants will provide greater than 93% power to demonstrate that each of the mesh augmented arms is superior to native tissue repair under the assumptions outlined above. Because randomization occurs prior to scheduling the surgery, some randomized patients may not receive surgery as a consequence of patient-related events occurring after randomization. To maintain power for the study, patients who are not treated within 6 months may be discontinued from the trial; enrollment will continue until a total sample size of 363 randomized and treated patients is reached.

After April 18, 2019, the study was closed to new surgeries of transvaginal mesh. The remaining 18 consented or randomized patients will be randomized to receive either sacral colpopexy or native tissue repair in a 1:1 ratio. This modification is expected to have minimal to no impact on the planned statistical power, given that the recruitment period had been extended from 2 years to 36 months (thereby increasing power), and the final sample size of the TVM group will be approximately 95% of the planned size, while the other two study arms are expected to meet or even slightly exceed the planned sample size.

M.2. Analysis Populations

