with the appropriate parametric or nonparametric statistical tests. We will first conduct a model-based analysis using an appropriate proportional hazards model that examines failure risk as a function of randomized treatment arm, with details of the modelling approach specified after masked data review and documented in the statistical analysis plan prior to data unmasking. As specified in the statement of hypotheses and further detailed in the statistical analysis plan, within each analysis population, this single model will be used to generate four hypothesis tests, as applicable. The first test will compare the hazard ratio of the transvaginal mesh arm to the mesh augmented sacrocolpopexy arm against the hypothesized non-inferiority margin of 1.93, followed by a test of superiority if non-inferiority is shown, while the other two hypothesis tests will compare the hazard ratio of transvaginal mesh and mesh augmented sacrocolpopexy, respectively, to native tissue repair against the hypothesized null ratio of 1.0. All model-based analyses will include terms for the stratification parameters used in the randomization.

A number of secondary outcome measures that include both continuous and binary measures will be collected periodically across the study. To account for missing data associated with differential follow-up time associated with the primary design, appropriate model-based approaches (linear mixed models for continuous outcomes and generalized linear models for binary measures) will be used to compare the effects of treatment. The approach for these secondary analyses will be included in the statistical analysis plan.

M.4. Futility/Stopping Rules

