# 9.4.2 Primary Efficacy Analysis: Model-Based Survival Analysis

This model-based approach will serve as the primary analytic method for testing the comparative efficacy of the three strategies for uterovaginal prolapse as it can control for study design and potentially confounding variables. To appropriately account for the interval censored and right censored nature of the primary outcome data, and potential violation of the proportional hazards assumption across the entire follow-up time, while controlling for study design and potentially confounding variables in assessing intervention effects, a piecewise exponential (PWE) survival model will be employed. The PWE survival model is a model in which the time scale is divided into *K* periods and the underlying hazard function, h(t), is assumed to be constant within each period such that  $h(t) = \lambda_k \exp(\beta \mathbf{X})$ , where  $\lambda_k$  is the hazard function for period *k*, and **X** is a matrix of explanatory

variables with vector  $\beta$  coefficients (Breslow 1974). This piecewise approach effectively eliminates the need to specify the distribution of the hazard function and satisfies the proportional hazards assumption if the underlying hazard is constant within each period.

Among subjects who experience a surgical failure, the time to surgical failure (primary outcome) will be interval censored (i.e. lower bound, upper bound where both bounds are non-missing and lower bound < upper bound). Subjects who do not experience a surgical failure will be right censored (i.e. non-missing lower bound and missing upper bound) at their last attended visit. Specifically, the censoring interval for implementation in interval censored analysis will be defined as follows:

- lower bound = number of months (i.e. months as intended the by visit schedule) from the surgical intervention to the *last attended visit where the subject was considered to be not a surgical failure* across all post-operative visits starting at the 6 month visit. As such, subjects who were surgical failures at the 6-month post-operative visit will have a lower bound of 1.5 months corresponding to the 6-week post-operative visit. Based on this definition, the lower bound for the primary endpoint of 3 to a maximum of 5 years can take any of the following values 1.5, 6, 12, 18, 24, 30, 36, 42, 48, 54, or 60 months.

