### Nonparametric Survival Analysis for Interval-Censored Data

This analysis will employ nonparametric maximum likelihood estimation (NPMLE) to estimate survival functions for interval censored data (censoring intervals defined as described above) stratified by randomized surgical intervention in a similar manner as the Kaplan-Meier estimator for right censored data, but also employs a combination of the EM and iterative convex minorant (ICM) algorithms to estimate the survival function in non-overlapping intervals (Wellner and Zhan, 1997) and multiple imputation is used to account for the uncertainty of ranking overlapping intervals across participants caused by missed visits. Standard errors of the survival curves and the covariance matrix for the generalized rank statistic will be generated with the multiple imputation method developed by Sun (2001). Pairwise comparisons of the surgical arms corresponding to the 3 a priori specified hypotheses testing for superiority as described above will be performed based on the generalized logrank test statistic and the corresponding variance-covariance matrix (Huang, Lee, and Yu, 2008). The log-log transformation will be used to calculate confidence intervals. The nonparametric survival analysis methods detailed above will be carried out using the ICLIFETEST procedure in SAS. The advantage of this approach is that it makes no assumptions about the distribution of the interval centered data and permits estimated survival curves to be non-monotonic (no proportional hazards assumption), although it is unable to adjust for study design and potential confounders. This analysis will primarily be used to confirm the results of the primary model-based efficacy analysis.

In addition, this analysis will serve as a way to check the assumed PWE model assumptions, particularly the proportional hazard assumption and specification of the constant underlying hazard across periods. The Kaplan Meier survival curves will be graphically evaluated to evaluate the choice of periods specified in the PWE model, should the PWE model not converge. The Epanechnikov kernel-smoothed hazard rates from the non-parametric interval-censored Kaplan-Meier analysis will be generated and graphically assessed for violation of the proportional hazard assumption.

The general structure of the SAS code that will be used is summarized below.

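### If hazards cross, SAP 9.4.2 leaves open which model decides non-inferiority and how the 1.93 margin carries over, and leaves this to be settled after unmasking

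*SAP*

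**What the plan says.** Protocol M.3 calls for a proportional hazards model, "with details of the modelling approach specified after masked data review and documented in the statistical analysis plan prior to data unmasking". SAP 9.4.2 names it: an interval-censored piecewise-exponential model with yearly pieces. All four hypothesis tests come from that one model.

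The section introduces the model as accounting for "potential violation of the proportional hazards assumption across the entire follow-up time". Under its proportionality heading it then says that the model assumes proportional hazards between arms, and tests this at 0.05. If the test fails, smoothed hazard curves for the three arms are drawn and studied. If they differ in size only, the average hazard ratio is kept. If they cross to a substantial degree, "alternative parametric models that better fit the relatively complex hazard structures will be explored and compared to the pre-specified primary model", and an addendum describes the new efficacy methods.

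SAP 9.4.3 adds a nonparametric (NPMLE and generalised log-rank) analysis to confirm the primary result. Its tests are "Pairwise comparisons of the surgical arms corresponding to the 3 a priori specified hypotheses testing for superiority". The same section gives descriptive pairwise risk differences at years 1, 2 and 3, including TVM against SC, with 95% intervals.

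**The concern.** The hazard curves are drawn by arm. SAP section 5 places efficacy analyses after database lock and unblinding, and the masked review in SAP 7.5 does not list a proportionality check. So in the crossing case, new efficacy models would be chosen by people who have seen the treatment contrast. That conflicts with the timing rule in Protocol M.3.

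Three things are undefined:

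- which model decides H1 (non-inferiority of TVM to SC);
- what quantity replaces a single hazard ratio, and so what the 1.93 margin means for it;
- how much crossing counts as substantial.

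H1 drives the sample size and carries 0.03 of the 0.05 total alpha. If the estimate that meets the margin can be picked afterwards, the 0.03 is no longer guaranteed. The confirmatory nonparametric test does not help, because a log-rank test against a ratio of 1 cannot confirm non-inferiority.

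**Working it through.** **1. The plan's own figure.** Inputs from Protocol M.1: "These 2-year success rates represent hazards of 0.1116 and 0.2554, respectively"; "this non-inferiority margin corresponds to a hazard ratio of 1.93"; "spend alpha of 0.03 using a one-sided non-inferiority test"; 121 per arm; 2 years' accrual (A), 3 years' further follow-up (F), 5% loss per year.

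- Margin: ln(0.65)/ln(0.80) = 1.93.
- Event probability with h = 0.1116, l = 0.05, t = h + l = 0.1616: (h/t) × [1 − (e^(−Ft) − e^(−(A+F)t))/(At)] = 0.6906 × [1 − (0.6158 − 0.4457)/0.3232] = 0.327. Over 242 patients this gives about 79 events.
- Power: Φ(½ × √79.2 × ln 1.93 − 1.881) = Φ(2.93 − 1.88) = 0.85. The stated 85% is reproduced.
- Total alpha: 0.03 + 0.01 + 0.01 = 0.05.

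**2. Ceiling under proportional hazards.** If the true ratio is a constant 1.93, other models come into play only when the 0.05 test rejects. False non-inferiority is then at most 0.03 + 0.05 = 0.08, whatever is done afterwards.

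**3. Simulation at a constant ratio of 1.93.** 6,000 three-arm trials, 121 per arm, six-monthly visits, 3 to 5 years' follow-up, planned hazards and loss. The documents name no alternative models and no crossing rule, so both are assumed. Crossing is any sign change in a fitted log hazard ratio between two arms, which is looser than the SAP's wording. The menu has 13 estimates: a time-varying effect read at four times, and early, late and average ratios with splits at 12, 24 and 36 months.

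| Event | Share of trials |
|---|---|
| Proportionality test rejects | 5.6% |
| Test rejects and any pair crosses | 5.1% |
| Test rejects and TVM and SC cross | 2.4% |
| False non-inferiority, fixed model only | 2.6% |
| False non-inferiority, one fixed replacement | 3.0% |
| False non-inferiority, best of the menu | 4.4% |
| Non-inferiority declared whenever both conditions are met, or by the fixed model | 7.5% |

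The simulation standard error is about √(0.03 × 0.97/6000) = 0.2 percentage points, so 2.6% and 3.0% are both compatible with 3%. Two separate runs gave 4.1% for the best of the menu against 3.2% for the fixed model (8,000 trials), and about 4.6% against 3.4%.

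**4. If hazards truly cross (assumed).** 1,500 trials each, with the early ratio set so that the primary model's average ratio is 1.93:

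| Early/late ratio, change point | Fixed model | One replacement | Best of menu |
|---|---|---|---|
| 2.5/1.0, 24 months | 2.7% | 17% | 37% |
| 2.8/0.5, 24 months | 3.6% | 48% | 82% |
| 2.2/0.5, 36 months | 3.1% | 10% | 22% |

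Here the quantity estimated changes along with the model, so these are not pure type I error rates for one hypothesis.

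**5. Checks on H1 that do not assume proportional hazards.**

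- In 2,500 simulated trials at a true ratio of 1.93, a log-rank test against 1 was non-significant at two-sided 0.03 in 15%. Absence of significance therefore cannot stand in for non-inferiority.
- The year 1 to 3 risk differences are not tied to 15 points. Their cumulative-failure denominator keeps anyone who has already failed but drops non-failures who missed the visit. SAP 7.3 reports more missed visits than usual because of COVID.
- A 2-year failure difference tested against 15 points (35% − 20%) with a one-sided 97% bound had 3.0% error at a ratio of 1.93 and 81% to 83% power at a ratio of 1. Those runs used Kaplan-Meier in place of NPMLE, and missed visits are not among their stated inputs.

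**The case against.** - **Replacement.** A reader might infer that the SAP lets the primary model be replaced. The text does not say so: alternatives are explored and compared, and all four tests come from the pre-specified model. SAP section 12 (Version 2) adds a 3-year analysis labelled post hoc and sensitivity, and names no replacement model. This stands. The defect is undefined status, not an instruction to replace.
- **Size.** A reader might let analysts choose freely in every trial among full, 3-year, 2-year and late-period analyses. That gives 4.3%, 5.7% and 7.1% as options are added. The SAP does not contain that procedure: a failed test and substantial crossing must both come first, and data cuts are not better-fitting parametric models. This stands.
- **No check on H1.** It would be too strong to say that H1 has no estimate free of proportional hazards. The risk differences in SAP 9.4.3 are adjusted for site and age, and their two-sided 95% upper limit is stricter than a one-sided 97% bound. This stands in part: they are descriptive, have no stated comparison with 15 points, and carry the denominator problem.
- **Contradictory description.** SAP 9.4.2 states the proportional hazards assumption plainly under its own heading. This stands, so aligning the opening sentence is an editorial matter.

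**Conclusion.** The point holds in this form: in the crossing case SAP 9.4.2 allows new efficacy methods to be written after arm-specific curves are seen, without saying which model decides H1 or how 1.93 carries over. That conflicts with Protocol M.3 and is more than missing detail, because following the SAP as written permits a choice of efficacy model after unmasking.

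The size is conditional. Under a constant ratio of 1.93, the error is about 3% with the fixed model or one fixed replacement, about 4% to 4.6% with the most favourable of several models, and 8% at most. These figures rest on an assumed menu and crossing rule. The much larger figures need hazards that truly cross, for which the documents give no evidence.

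The documents do not support a claim that the 3% error is inflated as a matter of course, or that the model was in fact replaced. Nothing here changes the sample size.

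**What to change.** - **SAP 9.4.2, decision model.** State that the pre-specified piecewise-exponential hazard ratio remains the sole decision model for all four hypotheses whatever the proportionality check shows, and that any later model is exploratory.
- **SAP 9.4.2, opening.** Align the sentence on violations of proportional hazards with the later statement that the model assumes proportional hazards between arms. Only the baseline is piecewise.
- **SAP 9.4.3.** Add, as a supportive check on H1, the NPMLE 2-year failure difference (TVM minus SC) with a one-sided 97% upper bound against 15 points, in the per-protocol population that is primary for H1. The arm-level estimates and standard errors are already planned: bound = difference + 1.881 × √(SE² for TVM + SE² for SC).

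Cost: SAP wording and one contrast. H1 alpha stays at 0.03, total alpha at 0.05 and power at 85%. The downsides are that a better-fitting model found later can only be exploratory, and that the NPMLE contrast is not adjusted for site or age.
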